6.4.1 Peripheral Blood Counts

6.4.1.1 Reappearance of blasts in the blood.

6.4.2 Bone Marrow Aspirate and Biopsy

6.4.2.1 Presence of > 5% blasts, not attributable to another cause (e.g., bone marrow regeneration).

6.4.2.2 If there are no circulating blasts and the bone marrow contains 5% to 20% blasts, then a repeat bone marrow performed \geq 1 week later documenting more than 5% blasts is necessary to meet the criteria for relapse.

Rev. 2/12 6.5 Leukemia Free State

6.5.1 Peripheral Blood Counts

6.5.1.1 No circulating blasts in peripheral blood by morphologic review.

6.5.2 Bone Marrow Aspirate & Biopsy

6.5.2.1 < 5% blasts, without clustering of blasts, and without Auer rods by morphologic review.

6.5.3 Flow Cytometry of BM Aspirate

Rev. 2/12 6.5.3.1 If one or more unique leukemia-associated immunophenotypes (LAIP) were identified at diagnosis, minimal residual disease (MRD) levels will be analyzed by multiparameter flow cytometry.

Rev. 2/12 6.5.3.2 Immunologic MRD must be below the level of detection (< 0.001) to qualify for "Leukemia-Free State".

Rev. 2/12 6.5.3.3 Any detectable immunologic MRD levels will be quantified and retrospectively correlated with relapse-free and overall survival.

6.5.4 Extramedullary leukemia must not be present.

6.5.5 If indeterminant, the BM Aspirate & biopsy should be repeated 1 week later.

6.6 Quality of Life Measurement

6.6.1 Assessment Battery

Patient reported outcomes measuring health related quality of life, physical and functional well-being, and fatigue are important components of a clinical trial. As the population of interest is elderly, it is also appropriate to perform a comprehensive geriatric assessment. Moreover, as the leukemia experience results in unique issues and concerns for patients, it is useful to choose an instrument that captures these unique issues.

6.6.2 Health-related Quality of Life

QOL will be assessed using the Functional Assessment of Cancer Therapy – Leukemia. This instrument combines the General version of the Functional Assessment of Cancer Therapy (FACT-G) with a

leukemia-specific subscale [100]. The FACT-G is intended to be a self-administered questionnaire that assesses four QOL domains: physical, social/family, emotional, and functional well being [101]. The FACT has been tested for reliability and validity. Test-retest correlation coefficients ranged from .82 (emotional well-being) to .88 (functional well-being) and .92 (total score) [101]. Convergent and discriminant validity were evaluated as well as construct validity. The FACT has good reliability and validity data, and has been shown to discriminate patients based on their stage of disease and performance rating as well as demonstrated sensitivity in detecting changes in QOL over time.

For this study, the Leukemia subscale will also be added to the FACT-G [100]. Comprised of 17 items, this subscale examines issues and concerns typically experienced by the leukemia patient population, such as "I am bothered by fevers; I worry about getting infections; and I feel isolated from others because of my illness or treatment." The Leukemia subscale is scored in the same manner as the FACT-G, so that higher scores reflect greater well-being; scores range from 0 – 68. Internal consistency is good (Cronbach's alpha 0.86-0.88). The Leukemia subscale was also successful in discriminating patients based on ECOG Performance status ratings, including the ability to detect changes in performance status over time.

The FACT Fatigue Scale has been developed by Cella and colleagues to assess the impact of fatigue on the multiple dimensions of QOL and will provide additional important QOL data in these patients [102]. The FACT Fatigue scale has been tested for reliability and validity with good results. Internal consistency was strong (alpha coefficient = .93-.95); convergent and discriminant validity were demonstrated by a strong positive relationship with other measures of fatigue and a strong negative relationship with vigor.

6.6.3 Comprehensive Geriatric Assessment

The abbreviated Comprehensive Geriatric Assessment (aCGA) is a brief, 15-item instrument developed from instruments used in the Comprehensive Geriatric Assessment: [103]. Specific items taken from known valid and widely used instruments: the Geriatric Depression Scale, the Activities of Daily Living, Instrumental Activities of Daily Living, and Mini-mental Status Examination; thus functional, emotional, and cognitive domains are represented. Specific item selection was based on highest item-to-total correlations in a retrospective review of 500 elderly cancer patients who had a Comprehensive Geriatric Assessment performed. Cronbach's α was 0.70-0.93. The aCGA is designed to function as a screening tool for use in the outpatient setting; patients who test positive should have more comprehensive testing [104]. Feasibility within the context of a clinical trial is high and can better capture the functionality of this patient population beyond the inclusion and exclusion criteria for this clinical trial. Moreover, it takes only 5 minutes to complete. For the proposed study, the aCGA will be augmented with the following

components: a brief nutritional assessment, social support assessment, co-morbidity, and sexual function.

6.6.4 Nutritional Status

Body Mass Index, a well-known and clinically used tool will be used to assess nutritional status for this trial. In a study of 214 elderly adults living in a community setting, a low BMI (< 22 kg/m²) was associated with dependency in ADLs and decreased survival at one year [105].

6.6.5 Unintentional Weight Loss

The percentage of unintentional weight loss is well documented as a prognostic factor in the context of chemotherapy treatment. Such weight loss occurring during the six months proceeding chemotherapy treatment was associated with a lower response rate to treatment, decreased performance status, and poorer survival [106,107].

6.6.6 Social Support

Medical Outcomes Study Social Support Survey:
Emotional/Information and Tangible subscales

These subscales from the MOS Social Support Survey [108] assess the expression of empathetic understanding and positive affect; the offering of information, advice, feedback, or guidance (emotional/information) and behavioral assistance or access to material aid (tangible). Twelve items, they are two of four subscales from the larger instrument. They have excellent internal consistency (Cronbach alpha ? 0.90); convergent validity was also demonstrated. All but one item uses a 5-point Likert scale. These scales were chosen as they are brief, relevant, and moreover, are part of the comprehensive cancer-specific geriatric assessment battery developed by Hurria and colleagues [109].

6.6.7 Co-Morbidity

The Comorbiity Questionnaire [110]. This instrument is a modification of the well-established Charlson Comorbidity Index (CCI) [111]. Designed to be a self-administered questionnaire; it identifies several medical conditions commonly encountered in the elderly patient population. It is scored like the CCI, which reflects not only the number of conditions, but the seriousness of each. Test-retest reliability was 0.91 (and 0.92 for the CCI [110]. The scale correlated significantly with health professionals' ratings via the CCI (Spearman correlation = 0.70) with item-specific agreement 90 – 100%, excluding the presence of tumor [110]. This instrument has not been extensively used in the elderly, nor in the oncology patient population, but the original Charlson Comorbidity Index has [112-114]. The CCI has demonstrated predictive value for evaluating tolerance for cancer treatment [112,113] an, in some studies, cancer survival [114]. For this study, the instrument will be modified to include some additional commonly occurring conditions (e.g. back pain, osteoporosis, depression, anemia) as well as some that commonly cause complications with AML management (chronic sinus infection, poor

dentition). The questionnaire will be further modified by asking the respondent to identify the number of medications taken, both prescribed and over-the-counter.

6.6.8 Sexual Function

Clinically, it has been observed that elderly AML patients who remain sexually active may better tolerate the rigor associated with induction therapy [115]. A literature review did not provide any data to support or refute this observation. Therefore, two additional questions related to sexual activity will be added to the Geriatric Assessment Battery but scored separately to address this important question.

Rev. 8/13, 12/13 6.7 Timing of QOL Assessment

The Geriatric Assessment Battery will be administered at the time of randomization for a baseline assessment. This battery includes the aCGA, Body Mass Index, Unintentional Weight Loss, MOS Social Support Survey (Emotional/Information and Tangible Subscales only), Comorbidity Questionnaire and Sexual Function.

The FACT-Leukemia and FACT –Fatigue instruments will be administered at the following time points:

- T1: Baseline before induction. (Beginning Step 1)
- T2: At day 14 (+/- 2 days) following 1st induction. (Nadir of Step 1)
- T3: Following the outcome restaging BM (day 35-56) prior to consolidation therapy. (End of Step 1, beginning Step 2)
- T4: At the beginning of randomization to Arm E or F. (Beginning Step 3)
- T5: At the end of the observation/maintenance decitabine (i.e. after 12 months) after randomization to Arm E or F). (End of Step 3)

NOTE: QOL is to be assessed at any time the patient is removed from or elects to withdraw from the study

For those patients who are eligible and elect to go on to transplant, the FACT-Leukemia and FACT Fatigue instruments will be administered at the following time points:

- T1_{tx}: At the beginning of the conditioning regimen
- T2_{tx}: 100 days (\pm 14 days) post transplant

Rev. 2/13 6.8 Timing of "ALESE" Questionnaire (see [Appendix V](#))

The ALESE questionnaire will be administered at patient registration, or during the first week of induction therapy, whenever possible.

Administration of the ALESE questionnaire at later dates is permissible in surviving patients.

NOTE: Return instructions for sites are in [Appendix V](#) on page 34.

7. Study Parameters

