Data coordination (including QA & secure data entry) will be performed in the Cancer Epidemiology program at Mayo Clinic, Florida. Patients will be given the self-administered ALESE questionnaire to complete within the first week of hospitalization on E2906, and the site research coordinator will return it to the investigator. A contact e-mail & telephone number will be provided in the questionnaire for questions and assistance to patients or site research personnel. While the ALESE questionnaire does not need to be completed immediately at baseline prior to initiating therapy (unlike the QOL correlative studies) - as it pertains to previous exposures and lifestyle/medical/family history factors which are stable - we will ask them to complete it in the first week of hospitalization to ensure that we can QA the questionnaire during their initial 1-month hospitalization. Also the ALESE questionnaire should optimally be completed within the first week of initiating therapy to minimize any potential bias of early mortality on the analysis.

High patient participation rates are anticipated, as in the earlier PALM study the case *Cooperation Rate* with the questionnaire was 83% (personal communication, [name]). Similarly, in E1Z03 (an unrelated QOL study) the compliance (with the help of close coordination and follow-up by a clinical coordinator) was >90% (personal communication, [name]). This is not expected to be a

significant additional burden for patients, and based on the experience from the PALM study it is anticipated that most patients will be able to complete the self-directed questionnaire in <20 minutes with minimal or no help (personal communication, [name]) unless they have extensive farm exposures (20-30 minutes). Indeed in the PALM study there was significant enthusiasm among patients to participate in the study (personal communication, [name]), and a similar response is anticipated in E2906. No additional laboratory or genetic studies are required, as appropriate leukemia & germline samples are already being collected.

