9.2 Primary Endpoint and Sample Size

The primary objective of this trial is to determine the effect of clofarabine on overall survival in comparison with standard therapy. The primary endpoint is overall survival (OS). OS is defined as the time between randomization and death from any cause. Patients last known to be alive at the time of an analysis will be censored.

The primary comparison of OS will be based on the treatment assignment received at randomization. To reduce potential bias of the primary comparison from the alloSCT arm, the patients will be censored at the time of allogeneic transplant for the primary analysis. Due to the potential confounding by maintenance therapy on the induction comparison, a weighted analysis (weighted Cox regression) (121,122,123) will be used for the primary analysis. Let π denote the actual proportion randomized to the observation arm of all patients entering on maintenance randomization. In the weighted analysis, patients who do not enter maintenance randomization get weight 1; Observation maintenance arm patients get weight $1/\pi$. Decitabine maintenance arm patients get weight 0. Thus, patients on the observed maintenance arm represent themselves as well as the response of $(1/\pi - 1)$ similar patients in the decitabine maintenance arm. A robust variance estimator that correctly accounts for the weights will be used in this setting.

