9.6 AML Clinical Epidemiology

We assume that approximately 600 (82% of all 727 registered to Step 1) patients will complete the ALESE questionnaire. The proportions of obese patients and patients who had benzene exposure, ever smoked in their lifetime, took aspirin regularly, took acetaminophen regularly, ever lived in rural/farm environments, or had other exposures or lifestyle factors will be calculated separately, along with their 95% CIs. With 600 patients, the width of the 95% CI will be no wider than 0.08.

We will examine the impact of smoking, obesity, regular acetaminophen use, regular aspirin use, benzene exposure, and living in a rural/farm environment on OS. The impact of some other exposures or lifestyle factors on OS will also be explored. Assume 50% patients ever smoked in lifetime and assume for those patients a 10% long-term cure rate and 8-month median overall survival in the non-cured group. With treatment arms combined, the study will have approximately 80% power to detect a 22% reduction in the hazard rate in non-smoking patients, using a one-sided log rank test at the significance level of 0.025 and assuming 2 years of follow-up. The number of events needed is 502. Assume 20% patients had benzene exposure and assume those patients have a 10% long-term cure rate and 7.5 -month median overall survival in the non-cured group. With treatment arms combined, the study will have approximately 80% power to detect a 27% reduction in the hazard rate in non- benzene- exposure patients, using a one-sided log rank test at the significance level of 0.025 and assuming 2 years of follow-up. The number of events needed is 482. When data are available, a one-sided log-rank test stratified by induction treatment effect will be used to evaluate the impact of those exposures or lifestyle factors on OS. Moreover, the weighted analysis as described in Section [9.2](#) will also be used in order to reduce the potential bias from the maintenance therapy. Patients receiving alloSCT will be included in this analysis.

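### Survivors may complete the ALESE questionnaire late while OS runs from randomization with no delayed entry; exposure hazard ratios are biased if lateness differs by exposure.

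*Combined protocol and SAP*

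**What the plan says.** - **Timing.** Section 6.8: "The ALESE questionnaire will be administered at patient registration, or during the first week of induction therapy, whenever possible". It then adds: "Administration of the ALESE questionnaire at later dates is permissible in surviving patients". No latest date is given. Footnote 20 to the Section 7.1 schedule also only prefers the first week.
- **Reason for early completion.** Section 1.6.5 says the form "should optimally be completed within the first week of initiating therapy to minimize any potential bias of early mortality on the analysis".
- **Time origin.** Section 9.2: "OS is defined as the time between randomization and death from any cause".
- **Test.** Section 9.6: "a one-sided log-rank test stratified by induction treatment effect will be used to evaluate the impact of those exposures or lifestyle factors on OS". The weighted analysis of Section 9.2 "will also be used in order to reduce the potential bias from the maintenance therapy". Neither analysis is given delayed entry, a landmark, or a rule for late completers.
- **Data available.** The Appendix V form asks for the date on which it is filled in.

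**The concern.** Being in the ALESE analysis requires a completed form, and a late form requires survival to that date. Counting such a patient as at risk from randomization adds person-time in which death was impossible, while patients who died before they could complete are absent. Section 1.6.5 recognises this hazard and handles it through early completion. Section 6.8 relaxes that safeguard, and Section 9.6 puts no analysis rule in its place.

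Two things are at stake. Survival among responders looks better than it is. And if one exposure group completes late more often, it gains more guaranteed time, which shifts the hazard ratio and the type I error of the tests under objective 2.2.9. Such an imbalance is possible: Section 1.6.5 notes that the self-administered form takes longer for patients with extensive farm exposure, and rural or farm living is one of the exposures tested.

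**Working it through.** **1. Reproducing the plan's figures (Section 9.6).** Smoking inputs: 50% exposed, 10% cured, 8-month median in the non-cured, HR 0.78 for non-smokers, one-sided 0.025, 80% power, 502 deaths. The Schoenfeld formula is d = (1.960 + 0.842)² / [p(1 − p)(ln HR)²].
- Smoking: 7.85 / (0.25 × 0.0617) = 509 deaths, against 502 stated; power at 502 deaths is 0.795.
- Benzene (20% exposed, HR 0.73): 7.85 / (0.16 × 0.0990) = 496 deaths, against 482 stated; power at 482 is 0.789.

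Expected deaths among 600 responders, all at risk from time 0, with 24 months' minimum follow-up and an assumed 48-month accrual, are 502.4 and 482.5. For smoking, accrual of 36 or 60 months gives 497 or 506. The stated numbers thus fit a calculation with no late entry.

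**2. How much time matters.** Under the smoker model, S(t) = 0.1 + 0.9 × 2^(−t/8), with t in months. This gives 0.981 at 1 week, 0.925 at 1 month, 0.794 at 3 months, 0.635 at 6 months and 0.418 at 12 months. For non-smokers, S(6) = 0.635^0.78 = 0.702. First-week completion is therefore almost harmless. Completion at 6 months would exclude about 37% of smokers and 30% of non-smokers, and would credit everyone left with 6 death-free months.

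**3. Effect on the estimate.** Simulation with the smoking inputs: 400,000 patients per scenario, late completion uniform from 0.25 month to a maximum, inclusion only if alive at completion, censoring uniform at 24-84 months. The late shares and delays are assumptions. HR is non-smokers to smokers.

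| Late: non-smokers / smokers, maximum delay | HR, from randomization | HR, delayed entry | Median OS (months), from randomization | Median OS (months), delayed entry |
|---|---|---|---|---|
| none | 0.779 | 0.779 | 10.7 | 10.7 |
| 10% / 10%, 6 months | 0.776 | 0.777 | 11.0 | 10.7 |
| 25% / 25%, 12 months | 0.775 | 0.778 | 12.1 | 10.7 |
| 50% / 50%, 24 months | 0.770 | 0.785 | 14.9 | 10.6 |
| 25% / 10%, 12 months | 0.742 | 0.780 | 11.6 | 10.6 |
| 10% / 25%, 12 months | 0.822 | 0.785 | 11.7 | 10.7 |
| 50% / 25%, 24 months | 0.677 | 0.783 | 13.3 | 10.4 |
| 25% / 50%, 24 months | 0.870 | 0.774 | 13.6 | 10.9 |
| No effect: 25% / 25%, 12 months | 1.001 | 1.003 | 10.6 | 9.4 |
| No effect: 25% / 10%, 12 months | 0.951 | 0.999 | 10.2 | 9.3 |
| No effect: 10% / 25%, 12 months | 1.049 | 0.999 | 10.3 | 9.4 |

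A smaller repeat (120,000 patients per scenario, 24-72 months' follow-up) gave 0.77-0.79 when lateness was unrelated to exposure, and about 0.75 or 0.82 for the 25% versus 10% imbalance.

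**4. What that does to the test.** With 502 deaths, √(502 × 0.25) = 11.20. An apparent HR of 0.951 under no effect gives a rejection rate of Φ(11.20 × 0.0502 − 1.96) = Φ(−1.40), about 8% instead of 2.5%. In the other direction, an apparent 0.82 in place of 0.78 lowers power from 0.795 to 0.604.

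**5. Prevalence.** If smoking has the assumed effect, 50% smokers at baseline become 0.635 / (0.635 + 0.702) = 47.5% among patients completing at 6 months. The overall shift is smaller when only some complete late. Delayed entry does not correct this.

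**The case against.** The strongest reply is that the exposure test is barely touched. Guaranteed time falls on exposed and unexposed responders alike. With lateness unrelated to exposure, even the 50%-late row moves the HR only from 0.78 to 0.770, and the standard error of log HR at 502 deaths is about 2/√502 = 0.089, so the shift is ln(0.78/0.770) / 0.089 = 0.15 standard errors. That stands. A reader might infer classic immortal-time bias in one group, or that the hazard ratios are distorted in general; the documents support neither.

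A reader might also infer that survival comparisons with the whole trial or with outside cohorts are invalid. Section 9.6 plans no such comparison and no median OS for responders. The outside comparison in Section 1.6.5 concerns the prevalence of exposures.

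Late completion is meant to be the exception. The schedule places the form before induction, and Section 1.6.5 plans quality checks during the first hospital month. The expected 600 responders of 727 (82.5%), set beside the 83% cooperation quoted from the earlier case-control study (0.83 × 727 = 603), leave almost no room for deaths before completion. This suggests that few late forms are expected, but it does not limit them.

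The ALESE text carries a Rev. 2/13 mark, which might suggest that patients enrolled before that date could only complete late. The documents do not state accrual before that date or whether those patients were approached, so no size is based on this.

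Finally, Section 1.6.5 refers to a detailed analysis plan within a grant application. It is not in these documents and may deal with entry time, so the fair statement is that Section 9.6 does not. Section 9.6 nevertheless already names the test.

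**Conclusion.** The point holds in a limited form. As written, late completers enter the OS analysis with survival time that was guaranteed by their inclusion. This inflates responders' absolute survival in every late-completion scenario. The exposure HR is materially biased only if late completion differs by exposure or by something linked to it: about 0.75 or 0.82 against 0.78, and about 0.95 or 1.05 under no effect, for an assumed 25% versus 10% late within 12 months. Larger imbalances do more. The late share and delays are not in the documents, so the sizes illustrate what could happen and do not predict it.

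Delayed entry recovers the true value in these simulations because lateness was random within exposure group. In practice it requires completion time to be independent of prognosis given the covariates. Patients too ill to fill in the form in week one could violate that.

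This is a cheap improvement. It concerns secondary objective 2.2.9 and leaves the primary OS comparison untouched.

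**What to change.** In Section 9.6:
1. Enter each patient into the risk set at the questionnaire completion date, with OS still measured from randomization, in both the log-rank or Cox analysis and the weighted analysis.
2. Report the distribution of completion times by exposure group.
3. Add a sensitivity analysis of OS and of the exposure proportions limited to first-week completers. It does not lean on the independence assumption for late forms, and it covers the prevalence estimates, which delayed entry leaves uncorrected.
4. State the independence assumption.

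The cost is an entry-time option in the analysis program and one extra table; the date is already on the form. Some early person-time is lost. No responder's death is lost, because every responder was alive at completion. The first-week analysis will be smaller than the full one by however many forms came in late.
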